6.2 IMPORTANT PROTOCOL DEVIATIONS

Data discrepancies and deviations from the CTP will be identified for all treated subjects.

Section 7.3 of the CTP: *Important protocol deviation (IPD) categories will be suggested in the IQRM plan, IPDs will be identified no later than in the Report Planning Meeting, and the IPD categories will be updated as needed.*

Consistency check listings (for identification of deviations of time windows) and a list of protocol deviations (e.g. deviations in drug administration, in blood sampling times, etc.) will be provided to be discussed at the Report Planning Meeting (RPM). At this meeting, all manual deviations identified at the sites by the CRAs and deviations too complex to program will be reviewed by the trial team to decide which are considered important. For definition of important protocol deviations (iPD), and for the process of identification of these, refer to the Boehringer Ingelheim (BI) SOP "Identify and Manage Important Protocol Deviations (iPD)" (2).

If any iPDs are identified, they are to be summarised into categories and will be captured in the decision log. Categories which are considered to be iPDs in this trial are defined in the integrated quality and risk management plan (IQRMP). An overview of the defined iPDs and if they could potentially lead to exclusion from defined analysis sets (see 6.3) is given in Table 6.2: 1. The decision on exclusion of subjects from analysis sets will be made at the latest at the Report Planning Meeting, after discussion of exceptional cases and implications for analyses. If the data show other iPDs, the definition in the IQRMP will be supplemented accordingly by the time of the Report Planning Meeting. The iPDs will be summarised and listed.

Table 6.2: 1 Important protocol deviations

Category/ Code	Description	Exclusion from
A	Inclusion/Exclusion Criteria	
A1	Inclusion Criteria Not Met	PKS
A2	Exclusion Criteria Violated	PKS
B	Informed consent	
B1	Informed consent not available/not done	TS / PKS
B2	Informed consent too late	none
C	Trial medication and randomization	
C1	Incorrect trial medication taken	PKS
C2	Randomisation not followed	PKS
C3	Non-compliance	PKS
C5	Incorrect intake of trial medication	PKS
C6	Improper washout between treatments	PKS
D	Concomitant medication	
D1	Prohibited medication use	PKS
E	Missing data	
E1	Certain deviations from procedures used to measure primary or secondary data	PKS

F		Incorrect timing	
	F1	Certain deviations from time schedule used to measure primary or secondary data	PKS
G		Other trial specific important deviations	
	G1	Incorrect intake of meal	PKS

6.3 SUBJECT SETS ANALYSED

Section 7.3 of the CTP:

- *Treated set (TS): The treated set includes all subjects who were randomized and treated with at least one dose of study drug. The treated set will be used for safety analyses.*
- *Pharmacokinetic parameter analysis set (PKS): This set includes all subjects in the treated set (TS) who provide at least one PK endpoint that was defined as primary or secondary and was not excluded due to a protocol deviation relevant to the evaluation of PK or due to PK non-evaluability (as specified in the following subsection 'Pharmacokinetics'). Thus, a subject will be included in the PKS, even if he/she contributes only one PK parameter value for one period to the statistical assessment. Descriptive and model based analyses of PK parameters will be based on the PKS.*

The two trial parts will be analysed separately, if not stated otherwise. Therefore, the two analysis sets will be split into TS/PKS of the Rosuvastatin part and TS/PKS of the Dabigatran part.

The primary and secondary analysis will be performed in the PKS. The PKS will also be used for the descriptive analyses of PD/biomarker parameters.

Section 7.3 of the CTP:

Pharmacokinetics

Plasma concentration data and parameters of a subject will be included in the statistical pharmacokinetic (PK) analyses if they are not flagged for exclusion due to a protocol deviation relevant to the evaluation of PK (to be decided no later than in the Report Planning Meeting) or due to PK non-evaluability (as revealed during data analysis, based on the criteria specified below). Exclusion of a subject's data will be documented in the CTR.

Relevant protocol deviations may be

- *Incorrect trial medication taken, i.e. the subject received at least one dose of trial medication the subject was not assigned to*
- *Incorrect dose of trial medication taken*

Plasma concentrations and/or parameters of a subject will be considered as non-evaluable, if for example

- *The subject experienced emesis that occurred at or before two times median tmax of the respective treatment (Median tmax is to be determined excluding the subjects experiencing emesis)*
- *A predose concentration is >5% Cmax value of that subject in the respective treatment period*
- *Missing samples/concentration data at important phases of PK disposition curve*

The descriptive analysis of PK concentrations will be based on the ADS ADPC as described at the beginning of [Section 7](#).

Table 6.3: 1 Subject sets analysed

Class of endpoint	Subject set	
	TS	PKS
Analyses of PK endpoints		X
Analyses of PD/biomarker endpoints		X
Safety parameters	X	
Demographic/baseline parameters	X	
Important protocol deviations	X	
Disposition	X	
Exposure	X	

6.5 POOLING OF CENTRES

This section is not applicable, because the study was performed in only one centre.

6.6 HANDLING OF MISSING DATA AND OUTLIERS

Handling of missing data and outliers will be performed as described in the CTP, Section 7.5.

The only exceptions where imputation might be necessary for safety evaluation are AE dates. Missing or incomplete AE dates are imputed according to BI standards (see BI-KMED-BDS-HTG-0035) (4).

Missing data and outliers of PK data are handled according to BI standards (see 001-MCS-36-472_RD-01) (5).

6.7 BASELINE, TIME WINDOWS AND CALCULATED VISITS

The baseline value is defined as the last measurement before trial medication administration in each treatment period.

Section 6.1 of the CTP: *Exact times of measurements outside the permitted time windows will be documented. The acceptable time windows for screening, the end of trial examination, and measurements and assessments scheduled to occur 'before' trial medication administrations are provided in the CTP Flow Chart.*

If not stated otherwise in the Flow Chart, the acceptable deviation from the scheduled time for the assessment of safety (e.g. vital signs, ECG, laboratory tests) will be ± 60 min.

For planned blood sampling times, refer to the Flow Chart. While these nominal times should be adhered to as closely as possible, the actual sampling times will be recorded and used for the determination of pharmacokinetic parameters.

If a subject misses an appointment, it will be rescheduled if possible. The relevance of measurements outside the permitted time windows will be assessed no later than at the Report Planning Meeting.

Adherence to time windows will be checked via the consistency check listings at the RPM.

Unscheduled measurements of laboratory data and vital signs data will be assumed to be repeat measurements of the most recent scheduled measurement (e.g. for follow-up or confirmation of a particular value). Therefore, unscheduled measurements will be assigned to the planned time point of the previous scheduled measurement.

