## FLOW CHART

### FLOW CHART PART 1 (ROSUVASTATIN)

Period	Visit	Day	Planned time (relative to drug administration) [h:min]	Approximate clock time of actual day [h:min]	Event and comment	Safety laboratory 	PK blood, Rosuvastatin	PK blood, BI 1323495	12-lead ECG	Vital signs (BP, PR)	Questioning for AEs and concomitant therapy 			
SCR	1	-21 to -1			Screening (SCR) 	X A			X	X				
1/2 (two identical periods separated by a wash-out of at least 7 days)	2/3	1	-2:00	06:00	Admission to trial site 	X B,2,3	X 	X 	X 	X 	X 			
			-0:30	07:30	Standardised breakfast									
			0:00	08:00	Drug administration									
			0:30	08:30					X 					
			1:00	09:00				X	X 					
			2:00	10:00	240 mL fluid intake			X	X 					
			3:00	11:00				X	X 					
			3:30	11:30				X						
			4:00	12:00	240 mL fluid intake			X	X 					
			4:30	12:30				X						
			5:00	13:00	Lunch 			X	X 				X	
			5:30	13:30				X						
			6:00	14:00				X	X 					
			7:00	15:00				X						
			8:00	16:00	Snack (voluntary) 			X	X 					
			10:00	18:00				X						
			11:00	19:00	Dinner									
			12:00	20:00				X	X 				X	
			2	24:00	08:00	Breakfast (voluntary) 			X B	X	X 	X	X	X
				28:30	12:30	Lunch (voluntary) 								X
32:00	16:00	Snack (voluntary)												
34:00	18:00	Discharge from trial site					X				X			
3	47:00	07:00	Ambulatory visit			X				X				
4	71:00	07:00	Ambulatory visit			X				X				
5	95:00	07:00	Ambulatory visit			X				X				
FU	4	8 to 15			End of trial (EoTrial) examination 	X C			X	X	X			

- Subject must be informed and written informed consent obtained prior to starting any screening procedures. Screening procedures include physical examination, check of vital signs, ECG, safety laboratory (including drug screening), [REDACTED] demographics (including determination of body height and weight, smoking status and alcohol history), relevant medical history, concomitant therapy and review of inclusion/exclusion criteria. [REDACTED]
- The time is approximate; the procedure is to be performed and completed within the 3 h prior to drug administration.
- Includes urine drug screening and alcohol breath test

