#### 5.2.3 Safety laboratory parameters

For the assessment of laboratory parameters, blood and urine samples will be collected by the trial site at the times indicated in the Flow Chart after the subjects have fasted for at least 10 h. For retests, at the discretion of the investigator or designee, overnight fasting is not required.

The parameters that will be determined are listed in Tables [5.2.3: 1](#) and [5.2.3: 2](#). Reference ranges will be provided in the ISF, Section 10.

Manual differential white blood cell count or urine sediment examinations will only be performed if there is an abnormality in the automatic blood cell count or in the urinalysis, respectively.

Faecal occult blood testing, using an immunochemical test kit for hemoglobin, will be performed by the laboratory at the time points indicated in the [Flow Chart for Part 2](#).

Table 5.2.3: 1 Routine laboratory tests

Functional lab group	BI test name [comment/abbreviation]	A 	B 	C 
Haematology	Haematocrit	X	X	X
	Haemoglobin	X	X	X
	Red Blood Cell Count/Erythrocytes	X	X	X
	White Blood Cells/Leucocytes	X	X	X
	Platelet Count/Thrombocytes (quant)	X	X	X
Automatic WBC differential, relative	Neutrophils/Leukocytes; Eosinophils/Leukocytes; Basophils/ Leukocytes; Monocytes/Leukocytes; Lymphocytes/Leukocytes	X	--	X
Automatic WBC differential, absolute	Neutrophil, absol.; Eosinophils, absol.; Basophils, absol.; Monocytes, absol.; Lymphocytes, absol.	X	--	X
Manual differential WBC (if automatic differential WBC is abnormal)	Neut. Poly (segs); Neut. Poly (segs), absol.; Neutrophils Bands; Neutrophils Bands, absol.; Eosinophils/Leukocytes; Eosinophils, absol.; Basophils/ Leukocytes; Basophils, absol.; Monocytes/ Leukocytes; Monocytes, absol.; Lymphocytes/Leukocytes; Lymphocytes, absol.			
Coagulation	Activated Partial Thromboplastin Time	X	X	X
	Prothrombin time	X	X	X
	INR (International Normalization Ratio)	X	X	X
Enzymes	AST [Aspartate transaminase] /GOT, SGOT	X	X	X
	ALT [Alanine transaminase] /GPT, SGPT	X	X	X
	Alkaline Phosphatase	X	X	X
	Gamma-Glutamyl Transferase	X	X	X
	Creatine Kinase [CK]	X	X	X
	Creatine Kinase Isoenzyme MB [only if CK is elevated]	X	X	X
Hormones	Thyroid Stimulating Hormone	X	--	--
Substrates	Glucose (Plasma)	X	--	X
	Creatinine	X	X	X
	GFR/ CKD-EPI 	X	X	X
	Bilirubin, Total	X	--	X
	Bilirubin, Direct	X	--	X
	Protein, Total	X	--	X
	C-Reactive Protein (Quant)	X	--	X
Electrolytes	Sodium	X	--	X
	Potassium	X	--	X

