Urinalysis (Stix)	Urine Nitrite (qual)	X	X	X
	Urine Protein (qual)	X	X	X
	Urine Glucose (qual)	X	X	X
	Urine Ketone (qual)	X	X	X
	Urobilinogen (qual)	X	X	X
	Urine Bilirubin (qual)	X	X	X
	Urine RBC/Erythrocytes (qual)	X	X	X
	Urine WBC/Leucocytes (qual)	X	X	X
	Urine pH	X	X	X
Urine sediment (microscopic examination if erythrocytes, leukocytes nitrite or protein are abnormal in urine)	Only positive findings will be reported (for instance, the presence of sediment bacteria, casts in sediment, squamous epithelial cells, erythrocytes, leukocytes)			

 A: parameters to be determined at Visit 1 (screening examination)  
 B: parameters to be determined at Visit 2 and 3 (for study days and time points refer to [Flow Chart](#))  
 C: parameters to be determined at Visit 4 (end of trial examination)  
 Estimated glomerular filtration rate according to CKD-EPI formula ([R12-1392](#))

The tests listed in Table 5.2.3: 2 are exclusionary laboratory tests that may be repeated as required. The results will not be entered in the CRF/database and will not be reported in the CTR. Except for drug screening, it is planned to perform these tests during screening only. Drug screening will be performed at screening and prior to each treatment period.

Table 5.2.3: 2 Exclusionary laboratory tests

Functional lab group	Test name
Drug screening (urine)	Amphetamine/MDA Barbiturates Benzodiazepine Cannabis Cocaine Methadone Methamphetamines/MDMA/XTC Opiates Phencyclidine Tricyclic antidepressants
Infectious serology (blood)	Hepatitis B surface antigen (qualitative) Hepatitis B core antibody (qualitative) Hepatitis C antibodies (qualitative) HIV-1 and HIV-2 antibody (qualitative)

To encourage compliance with alcoholic restrictions, a breath alcohol test (e.g. Alco True M®, [REDACTED]) will be performed prior to each treatment period, and may be repeated at any time during the study at the discretion of an investigator or designee. The results will not be included in the CTR.

The laboratory tests listed in Tables 5.2.3: 1 and 5.2.3: 2 will be performed at [REDACTED], with the exception of drug screening tests. These tests will be performed at the trial site using AccuSign® DOA 10 test or comparable test systems.

Laboratory data will be transmitted electronically from the laboratory to the trial site.

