7.8.2 Laboratory data

The analyses of laboratory data will be descriptive in nature and will be based on BI standards [BI-KMED-BDS-HTG-0042] ([10](#)).

Laboratory data will be analysed qualitatively via comparison of laboratory data to their reference ranges. Values outside the reference range as well as values defined as possibly clinically significant will be flagged in the data listings.

Clinically relevant findings in laboratory data will be reported as baseline conditions (at screening) or as AEs (during the trial) if judged clinically relevant by the investigator, and will be analysed as such.

It is the investigator's responsibility to decide whether a lab value is clinically significantly abnormal or not (at the RPM at the latest).

Descriptive statistics of laboratory data including change from baseline will be calculated by planned time point based on the worst value of the subject at that planned time point (or assigned to that planned time point).

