7.8.3 Vital signs

For vital signs (blood pressure and pulse rate), descriptive statistics including change from baseline will be calculated by planned time point based on the last value of the subject at that planned time point (or assigned to that planned time point). In the listing the difference from baseline will also be displayed.

Clinically relevant findings in vital signs will be reported as AEs.

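### SAP 6.7 files an unscheduled set B laboratory or vital-sign value taken after dosing at the pre-dose time point, so it drops out of the post-dose summaries

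*SAP*

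**What the plan says.** SAP 6.7 contains two rules.

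- Baseline: "The baseline value is defined as the last measurement before trial medication administration in each treatment period".
- Unscheduled laboratory and vital-sign values: they are "assumed to be repeat measurements of the most recent scheduled measurement (e.g. for follow-up or confirmation of a particular value"), and on that ground "unscheduled measurements will be assigned to the planned time point of the previous scheduled measurement". Whether a dose was given in between plays no part.

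Assigned values then enter the tables by planned time point. Laboratory summaries (SAP 7.8.2) are "based on the worst value of the subject at that planned time point (or assigned to that planned time point"). Vital-sign summaries (SAP 7.8.3) are "based on the last value of the subject at that planned time point (or assigned to that planned time point").

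The schedule comes from the protocol. Table 5.2.3: 1 has "B: parameters to be determined at Visit 2 and 3", the two treatment periods. In both flow charts the set B tests stand at -2:00 and at 24:00 on Day 2. For the -2:00 procedures a footnote adds that "the procedure is to be performed and completed within the 3 h prior to drug administration". Vital signs are marked at the same two times.

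Protocol 7.3.4 attributes measurements to treatments by the treatment in force at the planned time. SAP 6.1 presents the laboratory and vital-sign tables by on-treatment phase, and that phase begins at administration.

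**The concern.** The repeat convention is sound when the unscheduled value really repeats the scheduled one. It fails when the subject has been dosed in between, because the later value then reflects the treatment and the earlier one does not. With nothing scheduled for set B between the pre-dose sample and 24:00, the rule has only one place to send such a value: before the dose.

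At stake is the descriptive safety picture of the first day after dosing. A value obtained because something happened after drug intake would not count in any post-dose summary for that treatment, and might be shown as if it preceded the dose.

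**Working it through.** The plan gives no figure on this point, so the check applies the stated rules to the stated schedule.

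**Inputs.** Scheduled times in a period, in hours from dosing (both flow charts): set B laboratory {-2, 24}. Vital signs are {-2, 24} if the isolated marks at 5:00 and 12:00 belong to AE questioning, which is the likelier reading. The columns are shifted in the available text; if those marks are vital signs, the set is {-2, 5, 12, 24}.

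**Step 1: assignment.** Under SAP 6.7, assigned time = the latest scheduled time not after the actual time.

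| Actual time of unscheduled value (h) | Schedule {-2, 24} | Schedule {-2, 5, 12, 24} |
|---|---|---|
| 0.5, 1, 4 | -2 | -2 |
| 8 | -2 | 5 |
| 12 | -2 | 12 |
| 23.9 | -2 | 12 |
| 24.5, 34 | 24 | 24 |

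For set B laboratory tests the affected window is thus 0-24 h after dosing. For vital signs it is 0-24 h, or 0-5 h on the alternative reading. The upper end is the actual time of the next scheduled assessment, which may deviate by 60 minutes either way (protocol 6.1).

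**Step 2: treatment.** The planned time of the value is now -2:00. Under protocol 7.3.4 that lies before the first intake in period 1, hence in screening; in period 2 it lies in whatever phase preceded the second dose. In neither case is it attributed to the treatment just given.

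**Step 3: a pre-dose row, if one is shown.** The values below are made up, only to show how the selection rules act.

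| Measure | Pre-dose | Unscheduled, 4 h | 24:00 | Baseline (6.7) | Pre-dose row | Row minus baseline | 24:00 minus baseline |
|---|---|---|---|---|---|---|---|
| Systolic BP (last value) | 120 | 138 | 122 | 120 | 138 | 138 - 120 = +18 | 122 - 120 = +2 |
| ALT (worst value) | 25 | 60 | 30 | 25 | 60 | 60 - 25 = +35 | 30 - 25 = +5 |
| ALT (worst value) | 25 | 22 | 30 | 25 | 25 | 25 - 25 = 0 | 30 - 25 = +5 |

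For vital signs the post-dose reading always displaces the pre-dose one. For laboratory data it does so only when it is worse. Baseline and the 24:00 change stay the same throughout.

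**Step 4: can it happen?** Protocol 5.2.3 allows laboratory repeats without fixing a time: "For retests, at the discretion of the investigator or designee, overnight fasting is not required". Protocol 5.2.6.1.4, repeated in SAP 7.8.1, foresees an unscheduled blood test for AST, ALT and total bilirubin when symptoms of hepatic injury appear and no results are at hand. AST and ALT are set B parameters. Such a test responds to a new event and does not confirm an earlier value. Parameters outside set B, total bilirubin among them, are not part of this point.

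**The case against.** **The pre-dose row may not exist.** SAP 6.1 presents these tables by on-treatment phase, starting at administration, and a displayed pre-dose value could simply be the baseline. This stands: the mismatch with baseline depends on table layout, which the documents leave open. It does not help the value itself, which is then absent from the summary altogether.

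**The convention is deliberate.** A repeat of an unusable or doubtful pre-dose sample arguably belongs with that sample. That holds for a repeat drawn before dosing. A draw after dosing cannot confirm a pre-dose state, and a symptom-triggered test is no repeat at all.

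**Other safeguards cover such values.** Individual values are listed, out-of-range laboratory values are flagged, the vital-sign listing shows the difference from baseline, and clinically relevant findings become AEs. This stands and limits the harm to the summary tables, which are descriptive and carry no hypothesis test.

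**Further detail may exist elsewhere.** SAP 6.1 refers treatment handling to a technical analysis data set plan, and SAP 7.8.2 refers laboratory analysis to a sponsor standard. Neither was available, and either might add a dosing condition. Nothing in the protocol or SAP does.

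A reader might go further and infer that baseline is contaminated, that changes from baseline are biased, or that post-dose abnormalities are hidden from safety review. The documents support none of these. Baseline is fixed by order relative to dosing, so a post-dose value cannot enter it; the 24:00 change does not involve the misplaced value; and listings, flags and AE or AESI reporting do not depend on the assigned time point.

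**Conclusion.** The rule is wrong as written. Applied literally, it files an unscheduled set B or vital-sign value taken after dosing, and before the next scheduled measurement, at the pre-dose time point. The value is lost from the post-dose summaries and is not attributed to the treatment just given. For laboratory data this follows from the schedule without further assumption. For vital signs the length of the window depends on how the 5:00 and 12:00 marks are read. Disagreement with baseline arises only if a pre-dose row filled by the 7.8.2 and 7.8.3 rules is shown and, for laboratory data, only if the post-dose value is worse.

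The number of affected values cannot be estimated from the documents and may be zero, so no shift in a table mean is claimed. Primary and secondary PK endpoints are untouched. The change is optional.

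**What to change.** In SAP 6.7, limit the repeat-measurement rule to cases where no trial medication was given between the scheduled and the unscheduled measurement. Otherwise attribute the value by its actual time to the treatment just given, keep it out of any pre-dose summary, and include it in an on-treatment summary such as the worst on-treatment value. This does not conflict with protocol 7.3.4, because an unscheduled value has no planned time of its own. If the technical analysis data set plan already contains such a condition, stating it in 6.7 is enough.

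The cost is one sentence and a small derivation change. The summary will be sparsely filled and its mean and SD will say little; the listing remains the main source for these values.
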